5.6 Follow-up Phone Call

Participants will be contacted by a staff member within one week to assess whether they are having any symptoms.

5.7 Participant Withdrawal

Participants may decide to withdraw from the study at any point in time. Participants will be instructed to either write a letter or email their wishes to the Principal Investigator. The NIA will retain custody of the samples as outlined. The NIA is the exclusive owner of any data, discoveries or derivative materials from the sample materials and is responsible for the restriction of sample use at the participant's request. The samples collected in the study can be used by NIA investigators and their collaborators.

5.8 Early Termination Visit

The Principal Investigator may decide to take a participant off this study if it is believed to be in their best interest, if they fail to follow instructions, if new information becomes known about the safety of the study, or for other reasons the investigator believes are important. Participation in this study may be stopped at any time by the Principal Investigator without a participant's consent.

6 Study Procedures/Evaluations

Procedure	Screen	Visit 1	Visit 2	13 +/- 2 days post Visit 2	Visit 3
Informed Consent	X				
Review of Inclusion/Exclusion Criteria	X				
Medical History	X				
Physical Exam	X				
Height (cm) and Weight (kg)	X	X	X		X
Vital signs/orthostatic blood pressure measurements	X	X	X		X
CMP, ALT, AST, Alk. Phos., Total Bilirubin, CBC, Hepatitis B surface antigen, Hepatitis C, HIV and HbA1c, thyroid panel, cortisol level	X				
Urinalysis	X	X	X		X

Procedure	Screen	Visit 1	Visit 2	13 +/- 2 days post Visit 2	Visit 3
Blood samples for chemistry, lipids, oxysterols, lipodomics and exosomes (e.g., beta-amyloid)		X	X		X
CBC (Safety check)			X		X
Concomitant medication review	X	X	X		X
Insertion of venous catheter for frequent blood draws		X	X		X
Study medication (empagliflozin 25 mg daily)			X	X	X
Application of CGM		X	X		X
Diet Instructions / Record		X	X	X	X
Baseline blood and then frequent sampling (1.5-hours x 2, then q 1-hour x 1, then q 1.5-hours x 8, then q 2-hours x 4, then q 1.5-hours x 2, then q 1-hour x 1, then q 1.5-hours x 4. for β -hydroxybutrate (β -OHB), acetoacetate, fatty and amino acids, glucagon, insulin and glucose levels,		X	X		X
34-hour urine sampling for creatinine clearance, C-peptide and other hormones		X	X		X
MRS/MRI		X	X		X
Self-administration of study drug x 13 +/-2 days				X	
Meals/Snacks	X	X	X		X
Phone calls to monitor symptoms/compliance				X	
Adverse Event monitoring	X	X	X	X	X

6.1 Clinical Evaluations and MRI/MRS

Medical History and General Physical Examination

Participants receive a standardized physical exam and medical evaluation to include vital signs. Review of concomitant medications. This evaluation is required for study participation.

Body Measurements

Height and weight will be measured. These measurements are required for study participation.

Vital signs/Orthostatic blood pressures

This will be done to monitor for any problems of potential hypotension or dehydration.

Blood samples

Blood work for clinical chemistry, hematology, lipids, oxysterols, lipidomics, and exosomes will be done along with frequent blood sampling for hormones and ketones. An intravenous catheter will be placed for frequent sampling.

Safety Labs

Participants will have a fasting CMP/Lipid Panel on Day 1 of Visits 1, 2 and 3. On Visits 2 and 3 they will also have a CBC to monitor hemoglobin and hematocrit levels. Should a participant have a decrease of greater than 10% from the screening visit, the number of frequent blood draws would be decreased to every 2 hours. Therefore, the amount of blood taken on that visit would be approximately 130 ml (8.8 tablespoons).

Continuous Glucose Monitor (CGM)

The *Free Style Libre Pro* Continuous Glucose Monitor (CGM) device will be placed to measure interstitial glucose concentrations on Visits 1, 2 and 3. At the end of Visits 1 and 2 participants will wear the device until they return for Visits 2 and 3. The device will be removed at the end of Visit 3. The monitor consists of a small sensor that is inserted with a small needle and measures glucose levels just underneath the skin on the abdomen or the arm. The monitor will be inserted by the staff and the participant will be trained on wearing the device and who to call with questions or problems. A transmitter sends data wirelessly to the receiver. Once completed, data will be downloaded from the device to secure NIA servers.

Activity Monitor

On the evening of Day 1, participants will be given an activity monitor to wear on their wrist and will be instructed to walk approximately 2,000 steps. This will be done to try and keep activity levels similar in the 20 participants.

Study Medication

Empagliflozin (Jardiance) is an FDA approved drug used to treat type 2 diabetes. It is effective in lowering blood glucose levels in type 2 diabetic subjects, however, it is not known to lower blood glucose below normal levels (13). In other words, hypoglycemia is not a side-effect, it has not been reported to occur and is not therefore expected. An oral dose of 25 mg will be administered in the morning of days 1 and 2 of Visit 2. The participants will continue the study medication by self-administering for 13 +/- 2 days at home and recording on the medication log the time that they take their dose (Appendix G). The study medication will be discontinued at the end of Visit 3.

Diet Instructions/Records

Participants will be asked to record what they eat and drink during their inpatient visit on the Food Diary (Appendix C). They will be instructed on the importance of drinking 8 ounces of water every 4 hours, except when asleep. At discharge, they will be instructed to try and eat at the same times each day and record what time they eat or drink anything other than water on the Intake Diary (Appendix E).

Symptom Review Questionnaire

This will be used to assess the participant for any symptoms while taking the study medication. (Appendix I).

Compliance and symptom monitoring

Participants will be contacted daily between Visits 2 and 3 (during the days of self-administration of study drug) to ensure compliance and assess for any symptoms. We will also remind them about the importance of drinking water. It is imperative that participants do not miss 2 consecutive days of study medication or they will be excluded. The goal will be 100 percent compliance, however, greater than 90% will be acceptable.

Brain MRI: In total, structural MRI, fMRI and MRS will last about 1 hour.

- Structural MRI -- Standard structural brain images will be collected for coregistration, MRS voxel placement and to allow for clinical over-read.
- Resting state fMRI study in a single run. Subjects will be asked to keep their eyes open and fixate on a cross. This study will be used to assess intrinsic functional connectivity between different brain regions ⁶.
- MRS -- We will assess the concentrations of several brain metabolites, including glutamate, GABA, NAA, creatine, lactate, and glucose, using J-PRESS MRS in a voxel over bilateral precuneus, followed by fitting of metabolites using ProFit ⁶⁻⁸. Each of these metabolites has a characteristic pattern of spectral lines defined by the energy of transitions that occur when nuclei are excited into a higher energy state through radio frequency pulses. The spectral lines from all metabolites present, taken together, make up the observed spectrum. Concentrations of individual metabolites can be determined through evaluation of the relative sizes of the spectral lines in the observed spectra. The reliability of the measurement and fitting procedure for each metabolite can be assessed using Cramer-Rao lower bounds ⁹. We will use standard localization techniques based on magnetic field gradient sequences to obtain spectra from within the voxel of interest.

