4.4 Participant Exclusion Criteria (Screening Visit)

Exclusion Criteria:

- History of diabetes (requiring any medical treatment other than diet and exercise) or fasting plasma glucose > 126 mg/dl or HbA1c > 6.5 %.
- History of hypoglycemia.
- BMI > 35 kg/m².
- Creatinine clearance less than 60 ml/min as measured by GFR.
- Glucosuria
- History of anemia within the past 6 months or Hgb <11.0 mg/dL for women and Hgb <12.5 mg/dL for men.
- Current steroid use or steroid use within 90 days of screening, excluding eye drops.
- Currently taking loop diuretics (Lasix, for example).
- Participant presently following a calorie restriction diet, low carb/high fat diet.
- HIV virus infection

- Hepatitis B infection, as evidenced by a positive HBsAG at screen visit.
- Hepatitis C infection that has not been treated. (The screen blood work must show HCV RNA quantitative is not detectable).
- Active infection/fever that may cause changes in glucose metabolism.
- Known allergy to sGLT2 inhibitors in the past.
- Thyroid dysfunction that is not controlled or treated. This will be determined by Free T3, T4, Free T4 or TSH not within MedStar Harbor Hospital laboratory normal ranges for this pilot study.
- Adrenal dysfunction as determined by a cortisol level not within the normal range for MedStar Harbor Hospital Laboratory for this pilot study.
- Kidney or liver disease, (GFR < 60 mL/min/1.73 m² and/or liver enzymes not within normal ranges for MedStar Harbor Hospital Laboratory for this pilot study.
- Severe gastrointestinal diseases such as Crohn's disease or ulcerative colitis requiring continuous treatment.
- History of severe pulmonary disease such as chronic obstructive pulmonary disease (COPD) or asthma requiring continuous medication use.
- Patients with known, or evidence of, peripheral vascular disease.
- History of chronic urinary tract infections.
- History of recurrent or recent dehydration in the past year.
- History of recurrent or recent vaginal yeast infection.
- Alcohol intake greater than 30 grams (drink more than 2 beers OR equivalent per day).
- History of severe psychiatric conditions associated with behavioral problems or requiring chronic medical treatment.
- Poor venous access.
- Inability to walk 2,000 steps
- Donation or loss of 400 mL or more of blood within 56 days prior to and subsequent to screening.
- Participation in another study in the past 30 days, in which a study drug was administered.

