- a. Height/weight, orthostatic blood pressure measurements, pulse, temperature, respirations and pulse oximetry.
- b. I.V. placement for fasting blood tests (fasting for at least 8 hours) including CMP, CBC, lipids, insulin and other hormones, and exosomes. The study drug empagliflozin (Jardiance) will be administered at approximately 8:00 a.m. followed by blood sampling every 1.5 hours x 2, then q 1-hour x 1, then q 1.5-hour x 8, then q 2-hours x 4, then q 1.5-hours x 2, then q 1-hour x 1, then q 1.5-hours x 4 (completes 34-hours). This frequent sampling will include β -hydroxybutrate (β -OHB), acetoacetate, fatty and amino acids, glucagon, insulin and glucose levels. On Day 2, exosomes will be repeated and oxysterols and lipidomics will be drawn.
- c. Placement of a continuous glucose monitor (CGM) used to collect data for up to 14 days, worn by the participant until they return for Visit 3.
- d. 34-hour urine collection for creatinine clearance, C-peptide, and other hormones.

- e. Breakfast will be given within 30 minutes of dosing.
- f. All meals will be provided. They will aim to be consistent items and times as what was consumed on Visit 1. Participants will be asked to record the time and items they eat on a Food Diary (Appendix C). They will also be instructed to hydrate. This includes drinking 8 ounces of water every 4 hours except when asleep.
- g. On the evening of Day 1, the participants will be given an activity monitor and will be instructed to walk 2,000 steps before bedtime. They will be instructed when they are discharged to continue to walk 2,000 steps every evening while wearing the activity monitor. This will occur during the time they are taking the study medication at home.
- h. Day 2: Participants will receive empagliflozin (Jardiance) 25 mg followed by breakfast within 30 minutes.
- i. Brain MRS and limited brain MRI for voxel placement, required anatomical studies and resting functional connectivity will be conducted.
- j. Following the final blood draw, participants will be sent home and instructed on self-administration of a daily morning dose of empagliflozin (Jardiance) 25 mg and will wear the CGM until returning for Visit 3.
- k. Discharge instructions will be given (Appendix F). They will wear the CGM and be asked to complete an Intake Diary (Appendix E) to record consuming anything other than water to assist with the CGM data collection.

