7.1 Potential Risks

Risks of Blood Drawing and Intravenous (I.V.) insertion: The total amount of blood taken during a screening visit is up to 30 milliliters (ml) or 2 tablespoons. The total amount taken for Visits 1, 2 and 3 will be about 504 ml or 34 tablespoons. Participants may experience some discomfort and/or bruising at the site of needle entry. There is a remote chance of fainting or infection. The I.V. may need to be inserted if unable to obtain frequent blood samples.

Risk of Stored Samples: The greatest risk from the use of stored samples is the unplanned release of information from medical records. The chance that this information will be given to an unauthorized person without the participant's permission is very small. We will not enter any experimental information (research results) into any other medical record and we will not release information to a third party unless specifically authorized by the participant. Possible problems with the unplanned release of information include discrimination when applying for insurance and employment. Some problems may occur if a participant discloses information or he or she agrees to have his or her medical records released.

Risk of Hepatitis Virus B, hepatitis virus C, and human immunodeficiency virus (HIV) Testing: This study involves a number of blood tests that require the subject's blood be tested for blood-transmitted diseases such as hepatitis virus B, hepatitis virus C, and human immunodeficiency virus (HIV). If the participant is infected with HIV, hepatitis B (positive HBsAG) or C (HCV RNA quantitative is detectable), he/she will not be able to participate in this study. We will tell the subject what the results mean, how to find care, how to avoid infecting others, how we report these infections, and the importance of informing any partners of possible risk.

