Risks of Study Medication empagliflozin (Jardiance): The most common adverse reactions associated with administration of empagliflozin are dehydration, dizziness, lightheadedness, weakness, yeast and urinary tract infections. To decrease these risks, participants will be encouraged to hydrate and to maintain good hygiene. Other side effects may include low blood sugar, nausea, and upper respiratory tract infections. There also may be other side effects that we cannot predict, including hypersensitivity reaction. Rarely, sudden episodes of kidney injury may occur. Also, the Food and Drug Administration (FDA) has issued a warning about rare occurrences of a serious infection of the genital area (necrotizing fasciitis of the perineum) associated with sGLT2 inhibitors. Both of these have only been known in people who have diabetes. We will monitor for any symptoms during our daily calls to the participant while they are on study medication. This will include questioning any symptoms of tenderness, redness,

or swelling of the genitals or the area from the genitals back to the rectum. We will also monitor for fever or general feeling of being unwell.

Risks of Continuous Glucose Monitor (CGM): Potential risks include a slight skin irritation from the adhesive.

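### After entry the only haemoglobin rule is a fall of more than 10% from screening, so volunteers screened near the entry limit can drop below it with no protocol-required change

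*Combined protocol and SAP*

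**What the plan says.** Section 4.4, whose criteria apply at the screening visit, excludes anyone with "History of anemia within the past 6 months or Hgb <11.0 mg/dL for women and Hgb <12.5 mg/dL for men". The printed unit cannot be right for haemoglobin; I read g/dL throughout.

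Section 6.1 (Safety Labs) adds a CBC at Visits 2 and 3. The table in section 6 and section 6.2.1 agree. Section 5.5 does not list it for Visit 3, but I take it as planned. The rule attached to it is that, on a "decrease of greater than 10% from the screening visit, the number of frequent blood draws would be decreased to every 2 hours", with about 130 ml then taken at that visit. No other haemoglobin-driven action appears.

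Section 7.1 puts screening at up to 30 ml and adds: "The total amount taken for Visits 1, 2 and 3 will be about 504 ml or 34 tablespoons". The 34-hour schedule in section 5.4 includes "then q 1.5-hour x 8, then q 2-hours x 4, then q 1.5-hours x 2, then q 1-hour x 1".

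Other safeguards exist:
- orthostatic blood pressure at each study visit (6.1: "This will be done to monitor for any problems of potential hypotension or dehydration");
- daily calls and a symptom form while on drug at home;
- prompt communication of results that need follow-up (7.2);
- adverse-event reporting (9.1);
- unplanned visits at the study physician's request (10);
- the institute's monitoring plan (11.2);
- removal by the Principal Investigator (5.8).

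As described in the protocol, none of these names a haemoglobin value.

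**The concern.** A purely relative rule protects least the people with the least reserve. A man who falls from 16.0 to 14.3 (1.7/16.0 = 10.6%) has his sampling reduced while still 1.8 g/dL above the entry limit. A woman who falls from 11.0 to 9.9 (exactly 10%) does not, although she is 1.1 g/dL below hers.

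These are volunteers aged 55 or older in a study that section 7.2 says is not a treatment study, with safety monitored by the Principal Investigator and no monitoring board (11.1). Symptoms are a poor substitute for a threshold, because the drug's expected effects overlap with those of a low haemoglobin: "The most common adverse reactions associated with administration of empagliflozin are dehydration, dizziness, lightheadedness, weakness, yeast and urinary tract infections". The sponsor also treats blood loss of this order as material at entry: section 4.4 excludes donation or loss of 400 mL or more around screening, and the study's own draws come to about 30 + 504 = 534 ml.

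**Working it through.** **1. The plan's own 130 ml.** Assume the 504 ml is split equally: 504/3 = 168 ml per visit. The schedule is a baseline draw plus 2+1+8+4+2+1+4 = 22 timed draws, so 23 draws over 34 h. Every 2 hours gives 34/2 + 1 = 18 draws. Then 168 × 18/23 = 131 ml (or 168 × 17/22 = 130 ml without the baseline). This agrees with the stated figure and supports 168 ml per visit.

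**2. The unprotected band.** The rule is silent while on-study Hgb is at least 0.90 × screening Hgb. An untriggered fall below entry limit L is possible when screening Hgb < L/0.90.
- Women: 11.0/0.90 = 12.22. The lowest untriggered value from 11.0 is 0.90 × 11.0 = 9.9.
- Men: 12.5/0.90 = 13.89. The lowest untriggered value from 12.5 is 0.90 × 12.5 = 11.25.
- If Hgb is reported to 0.1 g/dL (assumption), the first values below the limits are 10.9 and 12.4. From 12.1 and 13.7 these are falls of 9.9% and 9.5% (no trigger). From 12.2 and 13.8 they are 10.7% and 10.1% (trigger). The bands are then 11.0–12.1 and 12.5–13.7.

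**3. Can study blood loss do this?** Before the Visit 3 CBC, about 30 + 2 × 168 = 366 ml has been taken. With blood volume B in ml (assumed; not in the protocol) and plasma volume restored, the fractional fall is 1 − (1 − 30/B)(1 − 168/B)².

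| B | No regeneration | Half regenerated |
|---|---|---|
| 3.5 L | 10.15% | 5.07% |
| 4.0 L | 8.91% | 4.46% |
| 4.5 L | 7.95% | 3.97% |
| 5.0 L | 7.17% | 3.58% |

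The fall reaches 10% only at B = 3.553 L or less with no regeneration. At 4 to 5 L it is 3.6 to 8.9%, always under the trigger.

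**4. Who would be below the entry limit at Visit 3 with the rule not fired (B = 5 to 4 L)?** Divide the limit by one minus the fall.
- No regeneration: women screened below 11.85 to 12.08, men below 13.47 to 13.72.
- Half regenerated: women below 11.41 to 11.51, men below 12.96 to 13.08.

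**5. What the 2-hourly switch saves and costs.**
- Blood: 168 − 130 = 38 ml per visit, which is 38/5000 = 0.76% to 38/4000 = 0.95% of blood volume. If it applies at both visits, the total for Visits 1 to 3 is 168 + 130 + 130 = 428 ml against 504 ml.
- Draws: 23 − 18 = 5 fewer. In hours 0–16, 11 timed draws become 8; after 24 h, 7 become 5; the draws at 18, 20, 22 and 24 h are already 2-hourly and stay.
- Matching: even hours coincide with the Visit 1 grid at 0, 4, 10, 16, 18, 20, 22, 24, 28 and 34 h. So 23 − 10 = 13 Visit 1 time points lose a same-time match. If the switch follows the 4-hour draw, the draws at 1.5 and 3 h are also kept and 11 are lost; that gives 19 draws, about 168 × 19/23 = 139 ml.

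**The case against.** The strongest reply is that clinical judgement already covers this. The Principal Investigator may remove anyone in their best interest, abnormal results have a follow-up route, and the institute's monitoring plan is not reproduced here and may require more. All of that stands. A reader might infer that the protocol obliges staff to keep sampling an anaemic volunteer; it does not. What is missing is a pre-specified prompt. The sponsor chose to pre-specify a haemoglobin rule, and the rule chosen passes over those nearest the limit.

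A reader might also take 9.9 and 11.25 as what study bleeding will produce. They are the edges of what the rule allows. At 4 to 5 L with half regenerated, 11.0 becomes about 10.5 to 10.6. The rule also follows a mention of both haemoglobin and haematocrit without saying which counts, so a haematocrit fall might fire it sooner; that test is still relative.

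Two further points stand. An entry limit is not in itself a stopping limit, so crossing it does not justify an automatic stop. And 2-hourly sampling spares little blood, with Visit 3 the last sampling visit, so blood saving alone would be a weak reason to change the plan.

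**Conclusion.** The point holds at low severity, as a cheap improvement. On the text, women screened from 11.0 to below about 12.2 g/dL and men from 12.5 to below about 13.9 g/dL can fall below the sponsor's own entry limit with nothing required by the protocol. A man at exactly 13.9 is outside the band, since 0.90 × 13.9 = 12.51 and the rule fires first.

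The band follows from the protocol's own figures. The claim that study bleeding can carry someone across the limit rests on assumptions: equal visit volumes, a 30 ml screening draw, blood volume of 4 to 5 L, restored plasma volume, and regeneration between none and half. No haemoglobin distribution is given, so the number affected among 20 is unknown and may be zero. Dehydration on the drug could raise measured haemoglobin and mask part of a fall; an absolute rule would share that weakness.

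The documents do not support a stronger conclusion that participants are left without protection or that sampling must stop at the entry limit.

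**What to change.** Reword the trigger in section 6.1 along these lines: *If, at Visit 2 or 3, Hgb is below 11.0 g/dL (women) or 12.5 g/dL (men), or has fallen by more than 10% from screening, the remaining draws are taken every 2 hours, and serial sampling continues only after a documented study-physician decision that considers orthostatic blood pressure and symptoms.* State whether a haematocrit fall also counts. Correct mg/dL to g/dL in section 4.4.

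The main benefit is the mandated, recorded review; the roughly 38 ml saved per visit is secondary.

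The cost is one paragraph, a Day 1 CBC result early enough to act on (laboratory turnaround is not given), and some data from those who cross the limit. They lose a net 5 of 23 draws, and 13 of 23 Visit 1 time points lose a same-time match (11 if the switch follows the 4-hour draw). That matters because the primary endpoint in section 3.2 compares Visit 3 with the participant's own Visit 1. The 18 to 24 h draws (2 to 8 a.m. with an 8 a.m. start) keep their match, but the 14.5 h draw (10:30 p.m.) does not, and the protocol does not define overnight. If the physician declines to continue, the remaining serial data for that visit are lost.

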3.2 Study Endpoints

The primary study endpoint will be the level of circulating ketones on Visit 3 with a target of 1.5 times that of the participant's baseline (Visit 1). Other outcomes will be secondary.

4 Study Population

Twenty participants, ten males and ten females, age 55 and older will complete this pilot study. The ceiling for this study (100) reflects the additional accrual that we may anticipate. If needed, the protocol will be amended to account for an increase in the number of participants needed to be recruited.

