- l. A staff member will phone participants daily to assure they are taking the study medication and to assess for any symptoms. We will also remind them about the importance to hydrate, as stated above (f).

5.5 Visit 3 occurs 13 +/- 2 days from Visit 2

At Visit 3, the enrolled participant will come to the NIA Clinical Research Unit for a two-day visit, lasting approximately 34 hours. The following procedures will be done:

- a. Height/weight, orthostatic blood pressure measurements, pulse, temperature, respirations and pulse oximetry.
- b. I.V. placement for fasting blood tests (fasting for at least 8 hours) including CMP, lipids, insulin and other hormones. The study drug empagliflozin (Jardiance) will be administered at approximately 8:00 a.m. followed by blood sampling the same as visits 1 and 2. Breakfast will be given within 30 minutes of dosing.
- c. Placement of a continuous glucose monitor (CGM) used to collect data for up to 14 days, worn by the participant until the end of Visit 3.
- d. 34-hour urine collection for creatinine clearance, C-peptide, and other hormones.
- e. All meals will be provided. They will aim to be consistent items and times as what was consumed on Visits 1 and 2. Participants will be also be instructed to hydrate. This includes drinking 8 ounces of water every 4 hours except when asleep.
- f. On the evening of Day 1, the participants will be given an activity monitor and will be instructed to walk 2,000 steps before bedtime.
- g. Day 2: Participants will receive empagliflozin (Jardiance) 25 mg followed by breakfast within 30 minutes.
- h. Brain MRS and limited brain MRI for voxel placement, required anatomical studies and resting functional connectivity will be conducted.

- i. Following the final blood draw, participants will have completed the study. They will no longer take the study medication or wear the CGM.
- j. Discharge instructions will be given (Appendix G).

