11.2 Safety Monitoring Plan

All protocols at the NIA follow the NIA Data and Safety Monitoring Plan. This includes using the Level of Risk Assessment Monitoring Guidelines that has been established for the NIA following NIH rules and regulations to ensure good clinical practices in the conduct of clinical research. Participants will be informed about new information from this or other studies that may affect their health, welfare, or willingness to stay in this study.

12 Statistical Considerations

This is a pilot study therefore no power calculation can be done.

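### Does the gap between the two-consecutive-day exclusion and the 90% compliance goal leave the primary ketone comparison undefined?

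*Combined protocol and SAP*

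**What the plan says.** Section 6.1 (compliance and symptom monitoring) makes two statements in succession. The first carries a consequence: "It is imperative that participants do not miss 2 consecutive days of study medication or they will be excluded". The second states an aim and a tolerance: "The goal will be 100 percent compliance, however, greater than 90% will be acceptable". The section does not say whether the percentage applies to each participant or to the study, which doses are counted, or what happens at or below 90%.

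Home dosing is described in Section 6.1 as "self-administering for 13 +/- 2 days at home" and in the Section 6 schedule as "Self-administration of study drug x 13 +/-2 days". Two doses are given in clinic at Visit 2. Section 5.5 gives a dose on the first morning of Visit 3 and another on the second: "Day 2: Participants will receive empagliflozin (Jardiance) 25 mg followed by breakfast within 30 minutes".

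Section 5.8 lets the investigator remove participants "if they fail to follow instructions". Section 4 plans for twenty completers, and Section 5.5 treats the last Visit 3 blood draw as completion. Sections 9.2 and 12.1 leave replacement to the investigator's discretion.

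The primary endpoint (Section 3.2) is within-person: "The primary study endpoint will be the level of circulating ketones on Visit 3 with a target of 1.5 times that" of the participant's own Visit 1 value. Section 12 opens with "This is a pilot study therefore no power calculation can be done" and otherwise covers enrolment and replacement. It names no analysis set.

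**The concern.** The two adherence statements appear to sort the same person differently. Someone who misses two doses on separate days does not trigger the exclusion rule, yet falls short of the stated tolerance. Unless removed, this person attends Visit 3 and supplies a full pair for the primary endpoint.

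The study is open-label and single-arm, and Section 12 is silent on the point. Whether the pair counts could therefore be decided after the ketone values are known. With 20 people, each would be 1/20 = 5 percentage points if the 1.5-fold target were summarised as a proportion reaching it. The result is meant to inform a larger study, so a choice made after seeing the data would be unwelcome.

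**Working it through.** **Inputs.** Home doses: 13 ± 2, so 11 to 15 (Section 6 schedule, Section 6.1). Clinic doses: two at Visit 2 and two at Visit 3 (Sections 5.4 and 5.5). Threshold: strictly above 90% (Section 6.1). Planned completers: 20 (Section 4). The plan gives no derived figure on this point to reproduce.

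**Step 1: compliance after m misses.** Compliance = (n − m)/n for n scheduled doses.

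| Doses counted | n | One miss | Two misses |
|---|---|---|---|
| Home doses as stated in Section 6.1 | 11–15 | 90.9–93.3% | 81.8–86.7% |
| Home doses if 13 ± 2 runs from Visit 2 Day 1 to Visit 3 Day 1 (interval minus 2) | 9–13 | 88.9–92.3% | 77.8–84.6% |
| Second row plus 4 clinic doses | 13–17 | 92.3–94.1% | 84.6–88.2% |
| First row plus 4 clinic doses | 15–19 | 93.3–94.7% | 86.7–89.5% |
| All 16 rows of the Appendix G log plus 4 clinic doses | 20 | 95.0% | 90.0% |

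Two misses exceed 90% only if (n − 2)/n > 0.9, that is n > 20, which the schedule never reaches. One miss passes when n > 10. It fails only if home doses number 9 (88.9%) or 10 (90.0%) and clinic doses are not counted.

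**Step 2: how many two-miss patterns the exclusion rule catches.** There are C(n,2) patterns, of which n − 1 are consecutive.

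- n = 11: 55 patterns, 10 consecutive, 45 not (82%).
- n = 13: 78 patterns, 12 consecutive, 66 not (85%).
- n = 15: 105 patterns, 14 consecutive, 91 not (87%).

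Read per participant, then, the in-between group exists on paper and contains most two-miss patterns.

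**Step 3: how many people that could be.** The documents give no miss rate. Assume independent misses with probability q per dose. The chance of at least two misses with none adjacent is the sum over m ≥ 2 of C(n − m + 1, m) q^m (1 − q)^(n − m). At n = 13, multiplied by 20 participants:

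- q = 1%: 0.0061 × 20 = 0.12 people.
- q = 2%: 0.0222 × 20 = 0.44.
- q = 5%: 0.1071 × 20 = 2.14.
- q = 10%: 0.2733 × 20 = 5.47.

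The answer is set almost wholly by the assumed q. Daily compliance calls, a dose log and a 100-dollar self-dosing payment (Section 10) point towards the low end.

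**Step 4: does the plan as written mislead the analyst?** Three provisions taken together give a default. Section 5.8 allows removal of a person who does not follow instructions. Section 5.5 says that finishing the Visit 3 draws completes the study. Section 4 counts completers. A person who was not removed and who finished Visit 3 is therefore one of the twenty and has a pair. Under that default, missed doses would if anything be expected to dilute a drug effect, though the documents give no figure for this. Both Visit 3 doses are scheduled in clinic, and the frequent sampling follows the first of them.

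**The case for a change.** The best case for a change is this. If falling to 90% or below were itself grounds for exclusion, the two-consecutive-day rule would add nothing, because two misses always fail the threshold. The statements must therefore do different jobs, and the person between them has no stated status. Section 5.8 is permissive, and neither it nor the replacement text says whether data already collected are analysed. The primary endpoint has a numerical target, and the two weeks of dosing exist to study prolonged inhibition, so adherence matters to the question. One sentence would settle it at almost no cost.

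Much of this is true. The arithmetic is sound, the denominator is unstated, and Section 12 names no set. Three things weaken the conclusion.

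- The statements are not contradictory. A consecutive-day rule can be applied during the daily calls, whereas a percentage is known only once dosing ends, so they can operate side by side. The percentage can also be read as a study-level goal, in which case no individual is left between them.
- Both an all-pairs set and an adherent set are defensible, and the data for either are already collected. Neither choice makes the other a mistake.
- No effect on the ketone ratio is shown, and there is no formal test whose outcome could turn on one or two pairs.

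Part of the medication instructions in Appendix F was not available for this review, so the absence of any further statement on missed doses cannot be claimed with certainty.

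**Conclusion.** No change is called for. The gap is real in the narrow sense that, read per participant, two scattered misses fall at or below 90% on every dose count the documents support (77.8% to 90.0%) without triggering exclusion. Its practical size cannot be derived from the documents and may be zero. Following the plan as written does not produce a wrong result: completers supply pairs, adherence is recorded, and a competent analyst would report all available pairs and describe any low adherence alongside them. What remains is missing detail in a 20-person uncontrolled pilot that specifies no formal analysis.

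This rests on two assumptions: that a completer's pair is kept by default, and that daily contact keeps scattered misses uncommon. If several completers did have low adherence, the reader would need to see that stated with the result, and the dose log and call records allow it. No view is taken here on which adherence rule should govern participation.
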